9.2 Sample Size Determination

Assuming that the treatment difference between the combo and naproxen alone of 6.5 and common standard deviation of 16.9 with respect to SPID₀₋₈, a total of approximately 528 subjects (144 subjects per active treatment arm and 48 in the caffeine and placebo using a 3:3:3:1:1 ratio) are required to achieve 90% of power with the type I error of 0.05, a total of approximately 556 subjects will be randomized into the study if a drop-out rate of 5% is assumed.

Page 44 of 67

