All participants are required to remain at the study center and complete all relevant assessments regardless of rescue.

Follow-Up Phase

Participants will be evaluated at a post-operative visit/call approximately 2-5 days after discharge for follow up for any adverse events or medications not known at the time of treatment.

The duration of each participant's participation will be approximately 37 days. See study schedule of assessment, table 1 below:

Table 1: Schedule of Assessment

Protocol Activities	Screening Visit	Dosing Inpa	Period tient	End of Trial Call or Visit
	(within 28 days prior to oral surgery)	Day 1	Day 2	(2-5 days after discharge)
Written Informed Consent	x			
Inclusion/Exclusion Reviewed	x	х		
Medical/Medication History (incl. caffeine consumption)	х	x		
Physical and Oral Examination	х			
Vital Signs ^a	x	x	x	
Urine for Drug Screen	x	x		
Breath or saliva alcohol test	x	x		
Dental x-ray examination	x			
Urine Pregnancy Test (if applicable)	x	x		
Admission to Unit		x		
Oral surgery (between 0530 h and 1030 h)		x		
Randomization Number Assigned		x		
Investigational Product Administration		x		
Surgical Trauma Rating		x		
Stop watch method (perceptible and meaningful relief)		x	x	
Categorical Pain Rating Scale ^b		x	x	
Pain Intensity Numerical Rating Scale (NRS) °		x	x	
Categorical Pain Relief Rating Scale °		x	x	
Global Assessment of Pain Relief ^d			x	
Concomitant Medications		х	x	x
Adverse Events Assessed	x	x	x	x
Discharge from Unit the afternoon/evening of Day 2			x	

^a vital signs (blood pressure, pulse rate, and respiration after sitting for at least 5 minutes). On Day 1, vital signs are due pre-operatively, post-surgery at 1 hour, 12 hours and on Day 2, 24 hours (-30 minutes pre-surgery; +30 minutes post-surgery; +/- 30 minutes from hours 1 through 24) after study medication dosing

^b to be completed prior to dosing

^c Pain Intensity NRS to be completed at baseline (predose), and Pain Intensity NRS and Categorical Pain Relief will be assessed 0.5, 1, 1.5, 2, 3, 4, 5, 6, 7, 8, 9, 10, 11, 12, 14, (16, 18, 20 if awake), 22 and 24 hours (+/-5 minutes over the first 8 hours; +/-8 minutes from hours 9 through 24) post-dose. If rescue occurs, scales/questions will be completed immediately each time rescue medication is taken ^d assessment will be completed immediately before first rescue medication is taken or at 24 hours post-dose

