3.1 Handling of Missing Data

3.1.1 Handling of Missing Data for Efficacy Assessments

Use of Rescue Medication:

In all analyses, for participants who take rescue medication, all pain intensity scores after intake of rescue medication will be imputed by the worse of the baseline or the score assessed immediately before taking rescue medication. All pain relief after intake of rescue medication will be imputed by "no relief" (0).

Missing data for efficacy parameter:

If Participants have missing pain data (i.e., pain intensity or pain relief scores) within the 24 hours period for the collection of pain rating data, but nonetheless complete the 24-hour period, then any missing timepoints will be replaced by a time-weighted average of the previous and the next available values (i.e., a linear interpolation for missing values) of the pain data (pain intensity / pain relief score). Intermittent missing data will only be imputed using linear interpolation method and if needed round down to the nearest whole number for pain relief scores, whereas for the categorical pain intensity the value will be rounded up to the nearest whole number.

Interpolation Formula,

$$y = \frac{y_2 - y_1}{x_2 - x_1} (x - x_1) + y_1$$

Where, and if needed round down to the nearest whole number for pain relief scores, whereas for the categorical paint intensity the value will be rounded up to the nearest whole number. y = missing pain data to be imputed, x = respective timepoint of y. y_1 and y_2 = pre and post available pain score of the missing pain data.

 x_1 and x_2 = respective timepoints of y_1 and y_2 .

If Participants do not complete the pain intensity/pain relief assessments for the full 24 hours, then the primary analysis will be calculated up to the last available timepoint, with no imputation for later timepoints.

In a sensitivity analysis, Participants who drop out of the study early because of a related AE or lack of efficacy will have later missing timepoints imputed using a worst-observation-carried-forward (WOCF) method, in which their worst observation at baseline or any time thereafter is imputed. For Participants dropping out early for any other reason, a last-observation-carried-forward (LOCF) imputation will be used.

No imputation will be done for missing data on stopwatch assessments of perceptible and meaningful pain relief. Instead, if data are missing for those assessments, data will be censored as described in Section 4.1.

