7.7 Efficacy Analysis

7.7.1 Primary Endpoint

The primary efficacy endpoint is the sum of change in pain intensity from 0 to 8 hours (SPID0-8). The treatment comparisons will be made in the following sequential order for SPID0-8 (each at 0.05 level of significance) in order to protect overall type 1 error at 0.05:

- Naproxen sodium/caffeine 220/65 mg versus Naproxen sodium 220 mg
- Naproxen sodium/caffeine 440/130 mg versus Naproxen sodium 220 mg
- Naproxen sodium/caffeine 220/65 mg versus Naproxen sodium/caffeine 440/130 mg

Once a comparison is statistically non-significant, the subsequent comparisons will be technically ineligible to be declared significant. However, all pairwise comparisons will be presented to provide a complete picture.

The primary efficacy endpoint is the summed pain intensity difference over 0 to 8 hours after Time 0 (SPID0-8). The formula for SPID0-8 calculation is presented in Section 4.1. The primary efficacy endpoint will be analyzed using an analysis of covariance (ANCOVA) model, which will include SPID0-8 as dependent variable, treatment as main effect and baseline pain intensity (Numerical Rating Score) as the covariate.

The least square (LS) mean, standard error (SE) and 95% confidence interval (CI) of LS mean for each treatment group will be reported.

In addition, the least square mean difference, SE, 95% Confidence interval of LS mean difference and p-value for all pairwise treatment group (include placebo) comparisons will be reported. Descriptive statistics (n, mean, SD, median, minimum, and maximum) for SPID0-8 will also be presented by treatment group.

ITT population (without imputation) will be used as the primary analysis for this primary endpoint while PP population (without imputation and single imputation) will be used as secondary analysis to conduct the sensitivity analysis.

In the primary analysis, endpoint will be imputed as described in Section 3.1.1, if any pain assessments are missing or Participant takes rescue medication.

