Endpoint	Statistical Method / Test	Analysis Populati on	Missing Data Imputation Approach	Parameters / Variables in the analysis (Stat. test/Model)	Analysis Time point
Primary Endpoint					
Sum of Pain Intensity Difference over 8 hours (SPID 0-8)	ANCOVA, Descriptive statistics	ITT	No imputation	Statistical Model: SPID0-8 as dependent variable, treatment as main effect and baseline pain intensity (Numerical Rating Score) as the covariate	8 hours
Sum of Pain Intensity Difference over 8 hours (SPID 0-8)	ANCOVA, Descriptive statistics	РР	No imputation and Single imputation	Same as Above	8 hours
Secondary Efficacy	Endpoint				
Sum of Pain Intensity Difference (SPID) from 0 to 2, 4, 6, 12 and 24 hours post-dose	ANCOVA, Descriptive statistics	ITT	No imputation	Statistical Models: SPID from 0 to 2, 4, 6, 12 and 24 as dependent variable, treatment as main effect and baseline pain intensity (Numerical Rating Score) as the covariate	SPID 0-2, 0- 4, 0-6, 6-12, 0-12, 12-16, 16-20, 12-24, 16-24 and 0- 24 hours
Sum of Pain Intensity Difference (SPID) from 0 to 2, 4, 6, 12 and 24 hours post-dose	ANCOVA, Descriptive statistics	РР	No imputation and Single imputation	Same as Above	SPID 0-2, 0- 4, 0-6, 6-12, 0-12, 12-16, 16-20, 12-24, 16-24 and 0- 24 hours
Total pain relief from 0 to 2, 4, 6, 8, 12 and 24 hours post-dose	ANCOVA, Descriptive statistics	ITT	No imputation	Statistical Models: TOTPAR from 0 to 2, 4, 6, 12 and 24 as dependent variable,	TOTPAR 0- 2, 0-4, 0-6, 6- 12, 0-8 0-12, 12-16, 16-20,

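### SAP 7.7.1 and the 7.7.3 table label the primary ITT SPID0-8 analysis as unimputed, although the governing rule imputes every post-rescue score; the label needs correcting and defining

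*SAP*

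**What the plan says.** SAP 7.7.1 describes the primary analysis in two ways. It first says "ITT population (without imputation) will be used as the primary analysis for this primary endpoint". It then says "In the primary analysis, endpoint will be imputed as described in" Section 3.1.1, and gives missing assessments or rescue use as the triggers. The 7.7.3 summary table, in its missing-data column, has "No imputation" for SPID0-8 in ITT. For the per-protocol (PP) set it lists an unimputed and a single-imputation version.

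SAP 3.1.1 sets three rules for pain scores:

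- **Rescue:** "In all analyses, for participants who take rescue medication, all pain intensity scores after intake of rescue medication will be imputed", using the worse of baseline and the pre-rescue score. Pain relief after rescue is set to zero. Protocol 9.4.1 has the same rule with the same scope.
- **Intermittent gaps** in participants who complete 24 hours: linear interpolation.
- **Early drop-out:** the primary analysis stops at the last available time. A sensitivity analysis uses WOCF or LOCF, depending on the reason for leaving.

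SAP 7.7.2 and 7.7.3 use the same labels for the secondary SPID and TOTPAR endpoints. Neither label is defined anywhere in the SAP. SAP 7.13 reports no changes to the protocol's analyses. On data collection, SAP 2.2 says "All participants are required to remain at the study center and complete all relevant assessments regardless of rescue".

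**The concern.** Read literally, the label and the rescue rule cannot both be followed for the primary endpoint. In many trials the slip would be harmless, because a participant who rescues has no later data. Here scoring continues after rescue, so a program with imputation switched off would run without error and return a plausible SPID0-8.

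That result would answer a different question. Under the rescue rule, a participant who needs rescue counts as having no benefit from then on. With observed scores, relief from ibuprofen or hydrocodone/acetaminophen counts for the assigned arm, and most for the arm that rescues most. The first contrast affected, combination 220/65 mg against naproxen 220 mg, heads the fixed sequence in SAP 7.7.1. If it is not significant, neither later comparison can be declared significant.

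**Working it through.** **1. What each rule does to the ITT SPID0-8**

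| Situation | SAP 3.1.1 | Literal reading of the label |
|---|---|---|
| Scores after rescue | Worse of baseline and pre-rescue score | Observed scores |
| Intermittent gap, 24 h completed | Linear interpolation | Left missing |
| Times after early drop-out | Not imputed in the primary analysis | Not imputed |

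Only the third row agrees, which suggests what the label was meant to cover. For later windows the second row also matters: the 16, 18 and 20 h scores are taken only if the participant is awake. A literal unimputed SPID16-20 would therefore lack scores by design for participants who sleep.

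**2. The plan's own sample size (Protocol 9.2)**

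Inputs: "Assuming that the treatment difference between the combo and naproxen alone of 6.5 and common standard deviation of 16.9"; "144 subjects per active treatment arm and 48 in the caffeine and placebo using a 3:3:3:1:1 ratio"; these "are required to achieve 90% of power with the type I error of 0.05". Sidedness is not stated.

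- n per arm = 2 × (1.960 + 1.282)² × (16.9/6.5)² ≈ 142.1, so 143 by the normal formula. The t-based solution is 143.03, which rounds up to 144. A one-sided test would need 116, so the plan is two-sided.
- Power at 144: SE = 16.9 × √(2/144) = 1.992; Φ(6.5/1.992 − 1.96) = Φ(1.304) = 0.90.
- Total: 3 × 144 + 2 × 48 = 528, and 528/0.95 = 555.8, so 556.

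The plan's figures reproduce. The labelling problem does not touch them.

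**3. One participant under each reading (assumed values)**

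SAP 4.1 defines SPID0-8 as the sum of (T_i − T_{i−1}) × PID_i. Take baseline 7, PID 0 up to 2 h, pre-rescue score 7 and rescue just after 2 h.

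- Rescue rule: every later score is 7, every PID is 0, and SPID0-8 = 0.
- Observed scores, with an assumed post-rescue PID of 2 to 5 at each of the six remaining hourly times: SPID0-8 = 6 × 2 = 12 to 6 × 5 = 30.

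**4. Shift in the combination-minus-naproxen difference (assumed values)**

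Assume that rescued participants in both arms have the same average observed PID and the same hours remaining, and that their imputed PID is 0. Zero is the highest value the rule allows. Then:

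shift = (naproxen rescue rate − combination rescue rate) × observed post-rescue PID × hours remaining to 8 h

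| Rescue gap | PID | Hours | Shift | 6.5 − shift |
|---|---|---|---|---|
| 0.05 | 2 | 4 | 0.05 × 2 × 4 = 0.4 | 6.1 |
| 0.10 | 3 | 5 | 0.10 × 3 × 5 = 1.5 | 5.0 |
| 0.20 | 4 | 6 | 0.20 × 4 × 6 = 4.8 | 1.7 |

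The last column takes 6.5 as the difference under the rescue rule. Protocol 4.3 reports 6.44 from the dose-ranging study but does not say how rescue was handled there.

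**The case against.** The strongest reply is that the documents already settle the rule. Protocol 9.4.1 and SAP 3.1.1 apply the rescue imputation to all analyses, SAP 7.7.1 names rescue as a trigger for the primary analysis, and SAP 7.13 declares no departures. No passage says that observed post-rescue scores enter SPID0-8. SAP 3.1.1 also treats rescue and missing data under separate sub-headings. The 7.7.3 column concerns missing data, and post-rescue scores are collected, so they are not missing. On this reading the label means no WOCF or LOCF after drop-out.

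Most of this stands. A reader might infer that the SAP sets up two competing primary estimands. The documents do not support that: they contain one governing rule and a label that contradicts it. Nor do they say that programmers will work from the 7.7.3 table; the table and listing templates are in a separate document.

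The reply does not make the label safe, for four reasons:

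- Interpolation is also imputation, and it is not confined to a sensitivity analysis.
- PP admits only participants who complete the 24-hour assessments. If single imputation means drop-out WOCF or LOCF, the two planned PP analyses would be nearly identical.
- SAP 7.7.2 calls PP secondary and then says that the secondary analysis is imputed, which can be read as leaving ITT unimputed.
- The same label stands against Peak PID, which SAP 4.1 defines on observed values. That invites reading the column as observed data.

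**Conclusion.** The contradiction is real and sits in the primary analysis. The rescue-imputed SPID0-8 with interpolation is the governing definition. The unimputed label is wrong as written, and probably means only that nothing is imputed after early drop-out.

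If the label were followed literally, the combination-minus-naproxen estimate would generally change when rescue differs between the arms. It would shrink if naproxen rescues more and grow if the combination does. The documents give no rescue rates or post-rescue scores, so the size is unknown. Under the assumptions above, the shift is about 0.4 to 4.8 points against the planned 6.5, with 1.5 in the middle case.

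A reader might also infer a definite loss of power. With the SD held at 16.9, the three cases would give power of 0.87, 0.71 and 0.13 at 144 per arm. This is not a finding. Replacing imputed runs with observed scores can change the SD as well as the difference, and the documents give no SD for that version.

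**What to change.** - In SAP 7.7.1, 7.7.2 and the missing-data column of 7.7.3, replace the unimputed label for ITT SPID and TOTPAR with: *Section 3.1.1 rescue rule and linear interpolation applied; no further imputation after early drop-out.*
- Define single imputation as the WOCF/LOCF drop-out imputation of 3.1.1. Run that sensitivity analysis in ITT, because PP holds only 24-hour completers, and reword the PP labels to match.
- If an analysis of observed post-rescue scores is wanted, list it separately as supplementary.

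The cost is SAP wording only, to be changed before unblinding. The rescue rule, data collection and the sample size (144 per main arm, 528 evaluable, 556 randomized) stay as they are.

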7.7.2 Secondary Endpoint(s)

Analysis of the secondary endpoints will be summarized according to the variable type. The details are presented in the following sections.

SPID from 0 to 2, 4, 6, 12 and 24 hours post-dose (SPID0-2, SPID0-4, SPID0-6, SPID6-12, SPID0-12, SPID12-16, SPID16-20, SPID12-24, SPID16-24 and SPID0-24)

SPID0-2, SPID0-4, SPID0-6, SPID6-12, SPID0-12, SPID12-16, SPID16-20, SPID12-24, SPID16-24, SPID0-24 will be calculated using the formula specified in Section 4.1. The same method that is used for the analysis of the primary endpoint will be used to assess the difference between the treatment groups in each metric.

This endpoint will be analysed using ITT population (without imputation) as primary analysis while PP population (without imputation and single imputation) will be used as secondary to conduct the sensitivity analysis.

In the secondary analysis, endpoint will be imputed as described in Section 3.1.1, if any pain assessments are missing or Participant takes rescue medication.

Total pain relief from 0 to 2, 4, 6, 8, 12 and 24 hours post-dose (TOTPAR0-2, TOTPAR0-4, TOTPAR0-6, TOTPAR 6-12, TOTPAR0-8 TOTPAR0-12, TOTPAR12-16, TOTPAR16-20, TOTPAR 12-24, TOTPAR16-24 and TOTPAR0- 24)

TOTPAR0-2, TOTPAR0-4, TOTPAR0-6, TOTPAR 6-12, TOTPAR0-8 TOTPAR0-12, TOTPAR12-16, TOTPAR16-20, TOTPAR 12-24, TOTPAR16-24 and TOTPAR0- 24 will be calculated using the formula specified in Section 4.1. These secondary efficacy endpoints will be analyzed using an analysis of covariance (ANCOVA) model, which will include TOTPAR as dependent variable, treatment as main effect and baseline pain intensity (Numerical Rating Score) as the covariate. The least square (LS) mean, standard error (SE) and 95% confidence interval (CI) of LS mean for each treatment group will be reported.

In addition, the least square mean difference, SE, 95% Confidence interval of LS mean difference and p-value for all pairwise treatment group (include placebo) comparisons will be reported. Descriptive statistics (including n, mean, SD, median, minimum, and maximum) for TOTPAR will also be presented by treatment group.

ITT population (without imputation) will be used as the primary analysis for this endpoint while PP population (without imputation and single imputation) will be used as secondary to conduct the sensitivity analysis.

In the secondary analysis, endpoints will be imputed as described in Section 3.1.1, if any pain assessments are missing or Participant takes rescue medication.

Time to First Use of Rescue Medication

Time to first use of rescue medication will be estimated and plotted using Kaplan-Meier method. Censoring will be applied as described in Section 4.1. Median time will be compared between the treatment groups and placebo using a log-rank test stratified by baseline pain intensity (Categorical pain intensity), pair wise comparison will be made using Tukey-Kramer method and adjusted P-value will be reported. The summary statistics (25th percentile, Median, 75th percentile and it 95% CI) and

K-M estimates of overall time to first use of rescue medication with 95% CI will be presented by treatment groups.

This endpoint will be analysed using ITT population as primary analysis and PP population as secondary to conduct the sensitivity analysis.

Cumulative proportion of participants taking rescue medication over the 24-hour period

Cumulative proportion of Participants taking rescue medication will be calculated as the cumulative number of Participants who takes rescue medication at given timepoint and percentage will be calculated by cumulative number of Participants who takes rescue medication at given timepoint divided by the number of Participants treated in respective treatment group.

The cumulative proportion of Participants taking rescue medication over 24-hours period will be presented using counts and proportion with timepoints $(0.5, \le 1, \le 1.5, \le 2, \le 3, \le 4, \le 5, \le 6, \le 7, \le 8, \le 9, \le 10, \le 11, \le 12, \le 14, \le 16, \le 18, \le 20, \le 22$ and ≤ 24 hours post-dose) by treatment groups and also curves over time will also be plotted by treatment group. The analysis will be performed for the ITT Population.

Participant will be counted only once in cumulative addition.

Time to achieve complete pain relief

Time to achieve complete pain relief will be analyzed similarly as for the time to first use of rescue medication.

It will estimate and plotted using Kaplan-Meier method. Censoring will be applied as described in Section 4.1. Median time will be compared between the treatment groups and placebo using a log-rank test stratified by baseline pain intensity (Categorical pain intensity), pair wise comparison will be made using Tukey-Kramer method and adjusted P-value will be reported. The summary statistics (25th percentile, Median, 75th percentile and it 95% CI) and K-M estimates of overall time to achieve complete pain relief with 95% CI will be presented by treatment groups.

This endpoint will be analysed using ITT population as primary analysis and PP population as secondary to conduct the sensitivity analysis.

Cumulative percent of participants achieving complete pain relief

Cumulative percentage of Participants achieving complete pain relief will be calculated as the cumulative number of Participants achieving complete pain relief at given timepoint divided by the number of Participants treated in respective treatment group.

The cumulative percentage of Participants achieving complete pain relief will be presented using frequency counts and percentage with timepoints $(0.5, \le 1, \le 1.5, \le 2, \le 3, \le 4, \le 5, \le 6, \le 7, \le 8, \le 9, \le 10, \le 10,$

 $\leq 11, \leq 12, \leq 14, \leq 16, \leq 18, \leq 20, \leq 22$ and ≤ 24 hours post-dose) by treatment groups and curves over time will be plotted by treatment group. Participant will be counted only once in cumulative addition. This analysis will be performed for ITT Population.

Time to first perceptible relief, time to meaningful relief, time to first perceptible relief confirmed by meaningful relief

Time to first perceptible relief measured by a stopwatch, time to meaningful relief measured by a stopwatch, and time to first perceptible relief confirmed by meaningful relief defined as the time to perceptible pain relief (the first stopwatch time) for those participants who had meaningful pain relief (the second stopwatch time) will be estimated and plotted using Kaplan-Meier methods.

The definitions and censoring rules are defined in Section 4.1. Median time will be compared between the treatment groups and placebo using a log-rank test stratified by baseline pain intensity (Categorical pain intensity), pair wise comparison will be made using Tukey-Kramer method and adjusted P-value will be reported. The summary statistics (25th percentile, Median, 75th percentile and it 95% CI) and overall K-M estimates with 95% CI will be presented by treatment groups. The analysis will be performed for the ITT Population.

Pain Intensity Difference (PID) and Pain Relief scores at 0.5, 1, 1.5, 2, 3, 4, 5, 6, 7, 8, 9, 10, 11, 12, 14, (16, 18, 20 if awake), 22 and 24 hours post-dose

The PID at each scheduled time point will be calculated using the formula specified in Section 4.1. Descriptive statistics (n, mean, SD, median, minimum, and maximum) will be presented by treatment groups.

Pain Relief score categories will be presented in the form of frequency counts and percentage by treatment groups and overall. Also, the pain relief score at each scheduled time point will be summarised using descriptive statistics (n, mean, SD, median, minimum, and maximum) by treatment groups. The analysis will be performed for the ITT Population.

A graphical illustration of the time effect curve (Time versus Mean PID / Mean pain relief score) will be presented.

Analysis of Peak Pain Intensity Difference (Peak PID)

The peak PID for each Participant will be identified using the description given in Section 4.1.

The Peak Pain Intensity Difference over the entire study (Peak PID0-24) will be summarized by treatment group using descriptive statistics (n, mean, SD, median, minimum, and maximum) and analyzed using an analysis of covariance (ANCOVA) model, which includes Peak PID0-24 as dependent variable, treatment as main effect and baseline pain intensity (Numerical Rating Score) as the covariate. The least square (LS) mean, standard error (SE) and 95% confidence interval (CI) of LS mean will be reported for each treatment group. In addition, the least square mean difference, SE, 95%

Confidence interval of LS mean difference and p-value for all pairwise treatment group (include placebo) comparisons will be reported. The analysis will be performed for the ITT Population.

Analysis of Peak Pain Relief

The peak pain relief for each Participant will be identified using the description given in Section 4.1.

The Peak Pain relief over the entire study (Peak Pain Relief 0-24) will be summarized by treatment group using descriptive statistics (n, mean, SD, median, minimum, and maximum) and analyzed using an analysis of covariance (ANCOVA) model, which includes Peak Pain Relief 0-24 as dependent variable, treatment as main effect and baseline pain intensity (Numerical Rating Score) as the covariate. The least square (LS) mean, standard error (SE) and 95% confidence interval (CI) of LS mean will be reported for each treatment group. In addition, the least square mean difference, SE, 95% Confidence interval of LS mean difference and p-value for all pairwise treatment group (include placebo) comparisons will be reported. The analysis will be performed for the ITT Population.

Cumulative percent of participants with 'at least a 2-point PID' over time

Participants with 2-point PID will be identified using the method mentioned in Section 4.1. The 2-point PID is the Participant PID which is greater than or equal to 2 at post baseline records.

Cumulative percentage of Participants with at least a 2-point PID will be calculated as the cumulative number of Participants with 2-point PID at given timepoint divided by the number of Participants treated in respective treatment group.

The cumulative percentage of Participants with 'at least a 2-point PID' will be presented using frequency counts and percentage with timepoints $(0.5, \le 1, \le 1.5, \le 2, \le 3, \le 4, \le 5, \le 6, \le 7, \le 8, \le 9, \le 10, \le 11, \le 12, \le 14, \le 16, \le 18, \le 20, \le 22$ and ≤ 24 hours post-dose) by treatment groups and curves over time will be plotted by treatment group. Participant will be counted only once in cumulative addition. This analysis will be performed for ITT Population.

Global Assessment of the investigational product

Global assessment of the investigational product ratings poor (0), fair (1), good (2), very good (3), and excellent (4) will be tabulated using frequency counts and percentage by treatment group. The p-value for the pair-wise treatment comparison will be calculated using Cochran-Mantel-Haenszel (CMH) test with modified ridit score controlling baseline pain intensity as strata, based on the proportion of subjects who have responded "Very Good" or "Excellent" that are grouped together.

This analysis will be performed for ITT Population.

Endpoint	Statistical Method / Test	Analysis Populati on	Missing Data Imputation Approach	Parameters / Variables in the analysis (Stat. test/Model)	Analysis Time point
Primary Endpoint					
Sum of Pain Intensity Difference over 8 hours (SPID 0-8)	ANCOVA, Descriptive statistics	ITT	No imputation	Statistical Model: SPID0-8 as dependent variable, treatment as main effect and baseline pain intensity (Numerical Rating Score) as the covariate	8 hours
Sum of Pain Intensity Difference over 8 hours (SPID 0-8)	ANCOVA, Descriptive statistics	РР	No imputation and Single imputation	Same as Above	8 hours
Secondary Efficacy	Endpoint				
Sum of Pain Intensity Difference (SPID) from 0 to 2, 4, 6, 12 and 24 hours post-dose	ANCOVA, Descriptive statistics	ITT	No imputation	Statistical Models: SPID from 0 to 2, 4, 6, 12 and 24 as dependent variable, treatment as main effect and baseline pain intensity (Numerical Rating Score) as the covariate	SPID 0-2, 0- 4, 0-6, 6-12, 0-12, 12-16, 16-20, 12-24, 16-24 and 0- 24 hours
Sum of Pain Intensity Difference (SPID) from 0 to 2, 4, 6, 12 and 24 hours post-dose	ANCOVA, Descriptive statistics	РР	No imputation and Single imputation	Same as Above	SPID 0-2, 0- 4, 0-6, 6-12, 0-12, 12-16, 16-20, 12-24, 16-24 and 0- 24 hours
Total pain relief from 0 to 2, 4, 6, 8, 12 and 24 hours post-dose	ANCOVA, Descriptive statistics	ITT	No imputation	Statistical Models: TOTPAR from 0 to 2, 4, 6, 12 and 24 as dependent variable,	TOTPAR 0- 2, 0-4, 0-6, 6- 12, 0-8 0-12, 12-16, 16-20,

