2.3 Determination of Sample Size

Assuming that the treatment difference between the combo and naproxen alone of 6.5 and common standard deviation of 16.9 with respect to SPID0-8, a total of approximately 528 subjects (144 subjects per active treatment arm and 48 in the caffeine and placebo using a 3:3:3:1:1 ratio) are required to

achieve 90% of power with the type I error of 0.05, a total of approximately 556 subjects will be randomized into the study if a drop-out rate of 5% is assumed.

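### The SAP does not define the pairwise statistic for its five time-to-event endpoints, and the most direct reading, contrasts of one five-arm log-rank test, is not valid for a pair at 3:3:3:1:1

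*SAP*

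**What the plan says.** SAP 7.7.2 words the test for time to first rescue as: "Median time will be compared between the treatment groups and placebo using a log-rank test stratified by baseline pain intensity (Categorical pain intensity". It continues: "pair wise comparison will be made using Tukey-Kramer method and adjusted P-value will be reported". The same wording is repeated for time to complete relief and for the three stopwatch endpoints (perceptible relief, meaningful relief, perceptible relief confirmed by meaningful relief). The table in SAP 7.7.3 repeats it for rescue and the stopwatch endpoints.

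SAP 2.3 fixes the arm sizes: "144 subjects per active treatment arm and 48 in the caffeine and placebo using a 3:3:3:1:1 ratio". Five arms give ten pairs. Six of these are 144 v 48, three are 144 v 144 and one is 48 v 48.

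Neither document gives the formula for a pair statistic. SAP 3 names SAS 9.3 or higher, but no procedure or option. Protocol 9.4.1 asks only for a log-rank test on these endpoints; the stratification and Tukey-Kramer appear first in the SAP.

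**The concern.** A k-sample log-rank test yields one score per arm, observed minus expected events, with the expectation taken from everyone still at risk in all arms. One log-rank test followed by Tukey-Kramer comparisons is most directly carried out on those scores: z = (U_j − U_k) / √(V_jj + V_kk − 2V_jk).

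Each U_j is a total that scales with arm size and measures the distance of arm j from the five-arm average. If all five curves coincide, every difference U_j − U_k is centred at zero. If only curves j and k coincide and the arms differ in size, it is not. Conversely, two different arms can have similar scores because one is three times the other's size. The p-value for a pair then depends on how the other three arms performed.

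The secondary objective (Protocol 3, SAP 2.1) compares the FDC with naproxen, caffeine and placebo on onset and duration. Four of the six 144-v-48 pairs are FDC v caffeine or placebo and fall within it. Naproxen v caffeine and naproxen v placebo are outside the objective, but they would be reported with adjusted p-values. A report could show naproxen sodium no better than placebo only because the FDC arms did well.

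**Working it through.** **Arm sizes.** The plan's own figures reproduce. With a "treatment difference between the combo and naproxen alone of 6.5 and common standard deviation of 16.9", n = 2(1.960 + 1.282)² × (16.9/6.5)² = 2 × 10.51 × 6.76 ≈ 142.1, so 143 per arm; 144 gives 90.4% power, two-sided. Then 3 × 144 + 2 × 48 = 528, and 528/0.95 = 555.8, so 556. This supports SPID0-8 only. No power, hazard or event count is given for a time-to-event endpoint, so all medians below are assumptions, in the order FDC one tablet / FDC two tablets / naproxen / caffeine / placebo.

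**Mechanism by hand.** Just after dosing, the expected score of arm j accrues at a rate proportional to n_j(h_j − h̄), with h_j = 1/median and h̄ = Σn_j h_j / Σn_j.

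*Medians 12/18/6/6/4 h (naproxen = caffeine true).* h̄ = (12 + 8 + 24 + 8 + 12)/528 = 64/528 = 0.1212.
- Naproxen: 144 × (0.1667 − 0.1212) = 6.55. Caffeine: 48 × (0.1667 − 0.1212) = 2.18. The difference is 4.36, where the pairwise null requires 0. With those two arms alone, h̄ = 32/192 = 0.1667 and the difference is 0.
- Placebo: 48 × (0.25 − 0.1212) = 6.18. Naproxen minus placebo is about +0.4, although placebo has 1.5 times the hazard. With those two arms alone, h̄ = 36/192 = 0.1875 and the difference is −3.0 − 3.0 = −6.0. The five-arm contrast has the wrong sign.

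*Medians 10/14/8/4/4 h.* h̄ = (14.4 + 10.29 + 18 + 12 + 12)/528 = 0.1263. Naproxen is 144 × (0.125 − 0.1263) = −0.19 and placebo is 48 × (0.25 − 0.1263) = 5.94, a difference of −6.1. The two-arm value is −9.0 (h̄ = 30/192 = 0.15625). By 16 h the expected numbers at risk are 47.5/65.2/36/3/3 and h̄ = 0.0996. Naproxen is then 36 × 0.0254 = 0.91 and placebo 3 × 0.1504 = 0.45, so the contribution has turned positive and cancels part of the earlier signal.

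**Simulation.** Two strata, exponential times, censoring at 24 h, 600 to 3,000 runs per case (standard error at most √(0.25/600) ≈ 2 points). Both methods use the Tukey critical value for five groups, |z| > 2.728, which is 0.0064 two-sided per pair. Entries are rejection rates.

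| Assumed medians (h) | Pair | Five-arm | Two-arm |
|---|---|---|---|
| all 8 | every pair (null) | 0.4–0.9% | 0.4–1.3% |
| 10/14/8/4/4 | naproxen v placebo | 2.8% | 90.4% |
| same | naproxen v caffeine | 2.6% | 91.4% |
| same | FDC 1 v placebo | 74.3% | 99.4% |
| same | FDC 2 v placebo | 100% | 100% |
| same | FDC 1 v naproxen | 14.7% | 17.2% |
| 10/14/8/8/4 | FDC 1 v placebo | 62.2% | 99.5% |
| same | FDC 2 v caffeine | 93.7% | 62.0% |
| 8/8/8/4/4 | all six 144-v-48 pairs | 55–60% | 90–93% |
| 12/18/6/6/4 | naproxen v caffeine (null) | 70.9% | 1.0% |
| 1.0/0.8/1.5/2.5/2.5 | naproxen v placebo | 6% | 58% |
| same | FDC 1 v placebo | 98% | 99% |
| complete relief 35/45/29/17/15% by 24 h | FDC 1 v placebo | 17% | 43% |
| same | FDC 2 v placebo | 94.5% | 87% |

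At 10/20/6/4/4 h the five-arm contrast declares naproxen v placebo significant in the wrong direction in 15% of runs. Repeat simulations of the 12/18/6/6/4 null gave 70% to 77%.

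**Cause.** With five equal arms of 106, the 10/14/8/4/4 case gives naproxen v placebo 95.6% v 98.0%, and at 10/14/8/8/4 the naproxen = caffeine null is rejected in 0.4% v 0.8%. Unequal allocation is the main cause. A check with all five arms equal would not reveal the fault.

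**The case against.** **The SAP does not say that pair statistics come from the five-arm test.** This stands. The log-rank wording could also mean each group against placebo, and a Tukey critical value can be applied to two-arm statistics, as it was above. If two-arm tests are intended, the fault disappears. But the text does not say so, and the same sentence is needed under either reading.

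**Not every 144-v-48 pair loses most of its power.** This also stands. A reader might infer that from the naproxen v placebo figures. Near-total loss arose only for naproxen v caffeine or placebo. The FDC pairs vary: almost no change in the early-relief case, 62% v 99.5% at worst for FDC one tablet v placebo in the rescue-type cases, and gains for some two-tablet pairs.

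**The hazards are invented.** True. At rescue medians of 9/10/8.5/2/2 h, naproxen v placebo is 96% v 100%. The naproxen = caffeine null shows that the test is invalid; it does not forecast the result, since the protocol describes naproxen sodium as an approved analgesic. Caffeine = placebo compares equal arms (48 v 48), so it stays centred and becomes conservative.

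**The consequences are limited.** Largely true. Kaplan-Meier curves and medians are shown for each arm, so a reversed sign would be visible. A reader might also infer that the trial's main conclusion, or the contribution of caffeine, is at risk. The documents do not support that: these endpoints are outside the SPID0-8 sequence in SAP 7.7.1, and FDC v naproxen has equal arms.

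**Conclusion.** The SAP should be changed here, though the trial's main result does not depend on it. The firm finding is that the pair statistic is unspecified and that its most direct reading does not test a pairwise null at 144 v 48. That follows from the algebra and needs no assumed hazards.

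The size does depend on assumed exponential hazards. Naproxen v placebo power can drop from about 90% to 3%, or from 58% to 6%, and a true naproxen = caffeine null can be rejected in about 71% of runs. Of the pairs in the secondary objective, FDC one tablet v placebo runs from no material change to a loss of 37 points (99.5 − 62.2). FDC two tablets v placebo changes little or gains in most cases; 8/8/8/4/4 h is the exception. FDC 220/65 v naproxen changes by 0 to 13 points. One v two tablets also stays centred but can lose a little more: about 5% v 21% at 1.0/0.8/1.5/2.5/2.5 h (1,000 runs).

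The point is about how the pair statistic is built. It would remain with no multiplicity adjustment at all.

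**What to change.** In SAP 7.7.2 (five endpoints) and the matching rows of 7.7.3, replace the pairwise wording with: *Each pairwise comparison will use a log-rank test stratified by baseline categorical pain intensity, restricted to the two arms being compared.*

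If adjusted p-values are wanted, name the adjustment and apply it to the two-arm p-values. Holm is one choice, because it needs no joint distribution of the ten statistics. Keep the five-arm stratified log-rank only as an overall test.

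The cost is SAP wording, a data-subset step in the program and the adjustment. No new data are needed, and no protocol change, because Protocol 9.4.1 specifies only a log-rank test.
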